## 7.0 Randomization and Masking

#### 7.1 Randomization

Enrollment in the study will be defined as satisfying all eligibility criteria and signing informed consent (see Section 9.4). Randomization to the two interventions being compared BIO and INJ) will not occur until patients have completed EMM and been classified as a non-responder based on showing a less than 75% reduction in the average frequency of solid, liquid, and/or staining FI events compared to the two-week baseline. See Figure 4 for Decision Tree governing patient flow through the study.

Randomization will occur in a ratio of 1:1 with an equal chance of being randomized to each treatment group. Randomization will be performed using randomly permuted blocks, with block sizes known only to the DCC, and will be stratified by clinical site and sex (male and female). For each participant, the web-based electronic data capture system will determine the treatment allocation from a static randomization table. Personnel at the clinical sites will not have access to the randomization table in order to minimize the risk of selection bias.

## 8.0 Statistical Considerations

## 8.1 Analysis of Primary Endpoints

Assessment of Randomized Treatment Response at 3 Months (Primary Efficacy Analysis). To test the efficacy of randomized treatment assignment, a generalized linear model with a logit link will be constructed to predict treatment response at 3 months post-randomization. Treatment group and the stratification factors of clinical site and sex will be included in the model as categorical independent variables. An ITT approach will be used in which participants will be analyzed based on their assigned treatment group regardless of actual treatment received. Participants without a valid bowel diary at 3 months due to drop out or other reasons will be classified as non-responders. Using this model, we will test the null hypothesis that the proportion of responders is the same in the two treatment groups at 3 months following randomization using an alpha of 0.05. Sensitivity analyses will be conducted to assess the impact of classifying participants with missing data as non-responders.

Assessment of Safety. The primary safety outcome is the percentage of participants in each randomized treatment group who experience an adverse event (AE) of pelvic pain of grade II or greater severity, treatment site infection, or a serious adverse event (SAE) requiring hospitalization between randomization and the 3 month assessment. Because the proportion of participants with one of these events is expected to be small, Fisher's exact tests will be used to compare the percentage of participants with a qualifying adverse event. The difference between the two treatment groups will be evaluated for significance using an alpha of 0.05. Participants who are missing safety data due to drop out or other reasons will be excluded from this analysis.

*Cost of Care Analysis.* Mean and median costs per participant will be estimated for each of the two treatment groups and from the perspectives of payers, patients, and society. We will analyze whether differences in costs through 3-month follow up across the intervention arms and perspectives are statistically significant using parametric t-tests or using non-parametric bootstrapping methods. We will evaluate differences between the two treatment groups using an alpha of <0.05.

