who respond to the nonspecific treatment components that are included in the EMM protocol may make it easier to detect differential effects of BIO and INJ. Patients who are responders to EMM will be followed up 3 months later; those who remain responders will be continued on EMM and be followed for the remaining 24 months of the study. However, those who are no longer responders to EMM after 3 months will be invited to be randomized to BIO or INJ just like patients who failed EMM at the end of the initial run-in treatment, and all outcome measures will be assessed at 3 months from initiation of the treatment arm to which they are randomized. They will be pooled with other patients randomly assigned to the same treatment for the primary analyses and will be assessed at 6 months. Those subjects will participate for 27 months.

- 3. *Randomly assigned treatment:* The window for treatment to be initiated is 0 days 4 weeks after randomization. Based on a randomization scheme implemented by the Data Coordinating Center, each patient will be randomly assigned to BIO or INJ and treated as follows:
  - BIO will consist of 5 required one-hour training sessions which should, ideally, be spaced at weekly intervals; however, the window between visits is 2 10 days to accommodate participants' schedules as long as no more than two visits occur in one calendar week. A 6th treatment session will be made available for patients if it is shown through anorectal manometry that they are having trouble understanding directions given during the first five sessions. These will occur in the 5-6 or so weeks following the initiation of treatment. Treatment approaches will include strength training in all patients, sensory training for patients with hyposensitivity, and/or urge-resistance training for patients with hypersensitivity to the sensations caused by rectal distention. Home exercises will be assigned to patients to practice these skills, and these will be guided by a brochure.

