Previous studies have identified a number of limitations to paper diaries: (1) Missing data if subjects forget to complete the diary or if it is illegible. (2) Inaccurate data that may result if subjects forget to record events when they occur and then try to remember what happened at the end of the day or several days later. In previous studies, we provided patients with a pocket-sized paper diary to take with them throughout the day and asked them to transfer their symptom ratings from the paper diary to a website at the end of the day. If they failed to submit a report to the website within 12 hours, they were sent an email reminder or were telephoned. They were also reminded the next time they attempted to enter data, if the data for the previous day was missing, and they were given an opportunity to report on the previous day; however, they were not permitted to go back further than the previous 24 hours. They were also provided with bonus payments for not missing any diary reports. With this combination of techniques, we were able to obtain an average of 73 consecutive days of symptom diaries without interruption from 185 IBS patients varying in age from 18 to 84. However, there is concern that since advancing age is a risk factor for FI, the patients who enroll in this study will be older and less comfortable than young or middle-aged subjects with transferring data to the internet. Therefore, to avoid biasing enrollment against these older subjects, we decided to use paper diaries for this study. To ameliorate potential problems with missing or untimely data reporting we will (1) thoroughly train subjects in recording their diary information at enrollment, and (2) telephone subjects during the first two weeks that they keep the diary to ensure that they are able to record events on this paper diary when they occur.

To protect against experimenter bias, patients will be classified as responders or non-responders based on diary data entered into the electronic data capture (EDC) system at the end of EMM and at 3-, 6-, 12-, and 24-month follow-up. Once the diary data are entered, a calculation performed within the EDC system will determine which patients are non-responders eligible for randomization, and the same process will determine which patients are non-responders at 3 months so they can be offered alternative treatment.

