#### 5.4 Estimated patient flow for this study

Figure 3 shows the estimated flow of patients through this study and identifies our assumptions regarding attrition. We estimate we will need to screen 855 patients because 2/3 will be ineligible or unwilling to be randomized. This leaves 285 to be recruited into the EMM protocol. Based on the Heymen study, we assume

15% attrition during this treatment phase and also assume that 20% (n=57) will be responders to EMM and therefore not eligible for randomization. This will leave 194 to be randomized (97 per group).

Figure 3 shows that we expect 78 from the BIO group to complete the 3-month assessment after allowing for attrition of 20% and we expect 92 from the INJ group to complete the 3-month assessment. (We assume attrition will be no greater than 5% for the INJ group because this is a low-burden treatment and also because patients will want to be screened for AEs related to INJ.) However, the statistical analysis will be by intent to treat (ITT) and will include all 194 randomized to treatment; patients who are lost to follow up prior to 3 months will be considered treatment failures. The number of patients we expect to be responders to each of the treatments at the 3-month assessment is based on the pivotal trials shown in Table 1. We separated them in this way in Figure 3 to be able to estimate the numbers of non-responders who are likely to choose an additional treatment option after 3 months. The expected number of non-responders eligible for an additional therapy at 3 months is 63 for the INJ arm^16 and 17 for the biofeedback arm^15. Assuming equal probability of choosing either of the 2 available options as an added or alternative treatment, we could expect 40 patients to choose the SNS treatment, 32 to choose BIO, and 9 to choose INJ. For the primary analyses of follow up at 6, 12 and 24 months, these non-responders will be retained in the ITT analysis as non-responders to their primary assignment at randomization. However, when we perform exploratory analyses of treatment combinations, these subjects will be treated as distinct groups and compared to patients who received monotherapy for the duration of the study. These comparisons (Aim D) are exploratory because there is insufficient power to test for significance. The left column of boxes in Figure 3 shows how we intend to follow up the responders to EMM.

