#### 6.1 Enhanced medical management

The key components of treatment are patient education about the basic physiological mechanisms

for defecation, diet and medication to normalize stool consistency, and pelvic floor exercises taught by printed instructions. This treatment will be tailored to the underlying bowel disturbance as evaluated by a 2-week baseline bowel diary and described Manual of Procedures.

We have previous experience with the design and testing of EMM. In an RCT of BIO, we developed a protocol for a conservative run-in prior to implementation of the BIO or pelvic floor exercise protocol. This conservative treatment protocol included educating patients about the basic physiology of continence and defecation by showing them videos of defecography examinations, teaching them to normalize stool consistency by adding fiber to their diet or taking antidiarrheal or laxative medications if needed, and teaching

them to use a daily symptom diary to chart their progress. By the end of this 4-week intervention, there was an average 60% reduction in frequency of FI, and 22% of patients reported adequate relief.

Subsequently, with the support of grant R01 HS018695 we enhanced the EMM protocol by giving it to a series of small groups of patients with FI and asking them for feedback on what they found helpful or difficult, and what suggestions they had for improvement. Then with the assistance of two consultants who were nurses with expertise on FI ([name] and [name]), we developed a pamphlet for explaining each step in the program to patients and a series of training videos to teach nurses how to provide this intervention. These data were adapted by [name] into a Standard Operating Procedure for EMM.

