Assessment of FI Severity. General linear modeling will be used to analyze change from baseline to 3 months in FI severity as assessed by the Fecal Incontinence Severity Scale (FISS). Independent variables in the model will include randomized treatment group, clinical site, and sex. Missing outcomes will be assumed missing at random for the purpose of this analysis, but sensitivity analyses will be conducted to test the robustness of the results to this assumption. The model will be used to estimate 95% confidence intervals for the change from baseline to 3 months in FISS score in each of the randomized treatment groups. In addition, longitudinal general linear modeling will be used to analyze change from baseline to 6, 12, and 24 months in FISS score. In addition to the independent variables used in the 3-month analysis, the model will include fixed effects for time and the interaction between treatment and time. The model will account for the lack of independence between multiple measures assessed over time on the same study participant by modeling the within-participant covariance structure. For the 6- to 24-month time points, 95% confidence intervals for change from baseline in FISS score will be estimated for responders in each randomized treatment group, as determined at 3 months, and separate estimates will be produced for groups of non-responders who select into each treatment combination. In this analysis, no formal hypothesis testing will be done, and confidence intervals will be compared descriptively.

*Fifty Percent Responder Rate.* The proportion of participants who have at least a 50% reduction in FI episodes will be modeled using the same methods described for the primary efficacy outcome. However, no formal hypothesis testing will be done, and p-values will be presented for informational purposes only. This will be analyzed for each follow-up assessment through 24 months.

*Continence Rate.* The proportion of participants who are continent at each follow up time point will be modeled using the same methods described for the primary efficacy outcome. No formal hypothesis testing will be done, and p-values will be presented for informational purposes only. This will be analyzed for each follow-up assessment through 24 months.

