Assessment of Disease-Specific Quality of Life. Change from baseline to 3 months, and to 6 through 24 months in the FI Quality of Life (FIQOL) scale will be analyzed using methods described for the analysis of FI severity.

Assessment of Anxiety, Depression, and Self-Efficacy for Managing Symptoms. Change from baseline to 3 months, and to 6 through 24 months in these Patient Reported Outcomes Measurement Information System (PROMIS) scales will be analyzed using methods described for assessment of FI severity.

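### The FISS and FIQOL change models leave out the outcome's own baseline score; adding it is a nearly free gain in precision, and diary covariates in the primary model are an optional extra

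*Combined protocol and SAP*

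**What the plan says.** **Secondary scales.** Section 8.2 analyzes FISS as change from baseline to 3 months with a general linear model: "Independent variables in the model will include randomized treatment group, clinical site, and sex". The 6- to 24-month version adds time and treatment-by-time. The same approach is carried over: "FI Quality of Life (FIQOL) scale will be analyzed using methods described for the analysis of FI severity". Neither model contains the baseline score. Table 2 and sections 4.2.1 and 4.2.4 have both scales completed at Baseline and again at the end of EMM. The Synopsis and Research objective 1 in section 1.1 plan to compare the arms on secondary scales; section 8.2 itself names confidence intervals for change within each arm.

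**Primary outcome.** Section 8.1 fits a logit model to 3-month response: "Treatment group and the stratification factors of clinical site and sex will be included in the model as categorical independent variables". Two diary counts already exist by then. Section 4.1.1 states that "a calculation performed within the EDC system will determine which patients are non-responders eligible for randomization", and section 7.1 admits to randomization only someone "classified as a non-responder based on showing a less than 75% reduction in the average frequency". Relapsing EMM responders also have a later qualifying diary: "However, those who are no longer responders to EMM after 3 months will be invited to be randomized to BIO or INJ" (section 3.0, item 2).

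**Other adjustment.** FI frequency appears as a candidate in the predictor analysis of section 8.3. The expectancy score is a planned covariate (section 3.0, item 7), but section 4.3.2 has it completed after treatment has started.

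**The concern.** A change score subtracts the whole baseline value, whatever the correlation between baseline and follow-up. Unless the regression of follow-up on baseline has slope 1, baseline noise is left in the comparison, and a baseline covariate removes it. At stake is the width of the intervals for FISS and FIQOL. This matters because Table 4 asks for 102 per group for a severity score, while section 5.4 expects only 78 and 92 participants to complete 3 months.

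For the responder outcome, the two diary counts show how far a participant stands from the 75% limit. With 20 episodes at baseline the limit is 0.25 × 20 = 5. Someone randomized at 6 episodes needs 1 fewer; someone randomized at 20 needs 15 fewer. If that distance predicts response, leaving it out gives up some power.

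**Working it through.** **1. The plan's own figures.**
- Section 5.2.1, taken as 40% vs 60%, two-sided 0.05, 80% power: n = [1.96·√(2·0.5·0.5) + 0.842·√(0.24 + 0.24)]² / 0.20² = 96.9, so 97. Reproduced.
- Table 4 severity score: difference 36 − 17.9 = 18.1, SD 45.8. n = 2·(1.96 + 0.842)²·45.8² / 18.1² = 100.5, so 101. The usual t correction adds 1.96²/4 = 0.96, giving 101.5, so 102 as stated.

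**2. FISS and FIQOL: between-arm saving.** Let s0 and s1 be the baseline and 3-month SDs and ρ their correlation. In large samples, adding the baseline score cuts the variance of the treatment difference by

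(s0 − ρ·s1)² / (s0² + s1² − 2ρ·s0·s1),

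which is never negative. With equal SDs it reduces to (1 − ρ)/2. The documents give neither ρ nor the SD ratio, so both are assumed.

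| ρ | saving, s0 = s1 | interval narrower by, 1 − √(1 − saving) | saving, s0/s1 = 0.7 |
|---|---|---|---|
| 0.3 | 35% | 19% | 15% |
| 0.5 | 25% | 13% | 5% |
| 0.7 | 15% | 8% | 0% |

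**3. FISS and FIQOL: per-arm means.** With equal arms, an adjusted arm mean is the overall mean plus or minus half the treatment difference. Each part carries half of the variance, and only the second shrinks. The saving in sampling variance is therefore half of that in step 2: 17.5%, 12.5% and 7.5%. Simulation gave 16%, 12% and 7%.

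**4. What this could mean with 78 and 92 completers.** Table 4 inputs serve as a guide only. The standard error is 45.8·√(1/78 + 1/92) = 7.05; 18.1/7.05 − 1.96 = 0.61, so power is about 73%. With the equal-SD savings it becomes 89%, 84% and 80% at ρ = 0.3, 0.5 and 0.7.

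**5. Responder model: power.** Simulation of 97 per arm, 60% vs 40% ITT response, five sites and sex, with 3,000 trials per scenario. Section 5.4 says "patients who are lost to follow up prior to 3 months will be considered treatment failures", so losses of 20% (BIO) and 5% (INJ) counted as non-response. The share of EMM improvement that lasts to 3 months was varied because the documents give no figure. Count distributions and treatment variability were also assumed.
- Planned model: 77.4% to 81.7% power over all scenarios, with and without these losses.
- Gain from the two log diary counts, in points: +0.3 to +3.6 (full carry-over), +0.1 to +1.5 (half), −0.5 to +0.2 (none). Monte Carlo SE of a gain: 0.24 to 0.53.
- In the setting matched to section 6.1, where "there was an average 60% reduction in frequency of FI, and 22% of patients reported adequate relief", the gain is at most +1.5.
- Type I error under six null scenarios: 4.7% to 6.2% as planned, 5.0% to 6.0% adjusted.

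**6. Responder model on the plan's expected flow.** Responders are 78 − 17 = 61 of 97 (BIO) and 92 − 63 = 29 of 97 (INJ), from Table 7 and section 5.4. Power is already about 99.7%, so at most 0.3 points are left to gain.

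**7. Responder model: interval.** In a separate simulation with 194 patients and two added covariates, one of them prognostic (assumed odds ratio per SD 1.5 or 2.0), the median SE of the log odds ratio rose from 0.303 to 0.313 and 0.325. Adjustment does not narrow this interval.

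**The case against.** The best case against is that this is a preference. Randomization is stratified by site and sex and the models adjust for both, so analysis matches design. Section 8.3 already models 3-month response with FI frequency as a candidate predictor. Section 8.2 reports per-arm intervals, for which the saving is only half as large. The correlations and the carry-over are assumed. The protocol stands at version 10.0, and responder rates by arm go to the DSMB (section 8.4), so a late change to the primary model invites questions.

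Most of this stands, and it is why the primary-model part is optional. It does not remove the point on FISS and FIQOL. The predictor analysis does not put a baseline score into those models, the Synopsis and section 1.1 do intend a between-arm comparison, and the large-sample saving cannot be negative.

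Three stronger readings are tempting, and the documents support none of them.
- *The primary test is biased or undersized.* It is valid, and 97 per group reproduces.
- *The trial is underpowered for FISS because 78 and 92 fall short of 102.* Table 4 uses percent decrease on the St Mark's or FISI score, not FISS, and the trial was sized on the responder outcome. The 73% in step 4 shows relevance; it is not an estimate for FISS.
- *Diary covariates would sharpen the odds ratio.* They would not (step 7); only test power can rise.

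**Conclusion.** The point holds as a modest improvement. For FISS and FIQOL, the baseline score lowers the between-arm variance by about 15% to 35% under equal SDs and correlations of 0.7 to 0.3. At an SD ratio of 0.7 the saving is 0% to 15%, and for per-arm means it is about half as large. The direction is certain in large samples; the size rests on correlations and SDs that the documents do not give.

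For the primary test the possible gain is roughly 0 to 4 points of power with the plan's attrition. It could be zero if EMM improvement does not last, and it is practically nil at the response rates the plan expects. Nothing here changes the validity of the primary analysis or its sample size.

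**What to change.** **Section 8.2 (main change).** Add the Baseline-visit FISS score as a covariate to the FISS change models and the Baseline-visit FIQOL score to the FIQOL change models, at 3 months and longitudinally. Name the Baseline visit explicitly: section 3.1 lets the Randomization Visit fall after randomization in the EDC, so only the earlier score is sure to precede allocation. Cost: one sentence and no new data. The PROMIS scales have no Baseline-column entry in Table 2, so their baseline timing is a separate question.

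**Section 8.1 (optional).** Prespecify log FI frequency from the pre-EMM diary and from the latest diary before randomization; for relapsing EMM responders the latter is the 3-month diary that led to randomization. The logs are always defined: entry needs at least 2 × 2 = 4 episodes in two weeks, and a reduction below 75% leaves more than 1, hence at least 2. Put these terms in the primary model only if the choice can be dated and documented as made without sight of results by arm, and then keep the site-and-sex model as a sensitivity analysis. Otherwise leave the planned model primary and report the adjusted one as the sensitivity analysis. In both cases give a standardized risk difference beside the odds ratio, because the adjusted odds ratio has a different meaning: in the simulations, the same 60% vs 40% gave a median of about 2.3 as planned and 2.3 to 2.7 adjusted. Cost: a short SAP amendment and its documentation.
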